## 9.4 Monitoring for Futility to Assess Prevention Efficacy

The objective of monitoring the trial for futility to assess PE is to monitor progress toward the minimal needed target number of treatment arm-pooled HIV-1 primary endpoint infections by the Week 80 visit in the MITT cohort. Two targets are monitored for:

1. the total number of HIV-1 infections needed to achieve the planned 90% power to detect  $PE = 60\%$ , and
2. the total number of HIV-1 infections needed to achieve 50% power to detect  $PE = 60\%$ ,

each using a 1-sided 0.025-level Wald test of  $H_0 : PE \leq 0\%$  against  $H_1 : PE > 0\%$ , assuming proportional hazards of HIV-1 infection in the pooled VRC01 and control groups. The target numbers in 1. and 2. are 57 and 21, respectively (calculated by solving equation (1) in Schoenfeld (1983)). The rationale for considering the two targets is as follows: (i) if the trial cannot achieve the planned 90% power to detect  $PE = 60\%$ , considerations about enrollment modification or expansion are warranted, and (ii) if the trial cannot achieve even 50% power to detect  $PE = 60\%$ , considerations about completing the trial early for futility to assess PE are warranted.

Two versions of the futility monitoring report will be generated. A report provided to the DSMB will be included in 6-monthly closed DSMB reports, starting in November 2017 for HVTN 703/HPTN 081 and in April 2018 for HVTN 704/HPTN 085, and will report:

- (a) the estimated distribution of the total (i.e., treatment arm-pooled) number of HIV-1 infections, with corresponding power to reject  $H_0 : PE \leq 0\%$  using a 1-sided 0.025-level Wald test under the alternative hypothesis  $PE = 60\%$  throughout the trial,
- (b) the estimated probability that the total number of HIV-1 infections is  $\geq 57$  (target 1) with 95% credible intervals,
- (c) the estimated probability that the total number of HIV-1 infections is  $\geq 21$  (target 2) with 95% credible intervals,
- (d) the estimated distribution of the number of HIV-1 infections in each of the three treatment arms.

The distributions in (a) and (d) will also be summarized by the mean number of HIV-1 infections with a Wald 95% confidence interval. The estimation procedures for (a)–(d) will be conducted under each of the following three scenarios:

- (i) the treatment arm-pooled infection rate in (a)–(c) and the three treatment arm-specific infection rates in (d) used for generating future data are based on a Bayesian model and the prior assumption that  $PE = 60\%$  (the design alternative),
- (ii) the treatment arm-pooled infection rate in (a)–(c) and the three treatment arm-specific infection rates in (d) used for generating future data are based on a Bayesian model and the prior assumption that  $PE = 0\%$  (the null hypothesis), and
- (iii) the treatment arm-pooled infection rate in (a)–(c) used for generating future data is based on a Bayesian model and the prior assumption that the infection rate equals the observed to-date infection rate.

The reason for conducting the estimation procedure under (i)–(iii) is that the purpose of the results for the 57 endpoint target (b) is to trigger considerations about enrollment modifications, whereas the purpose of the results for the 21 endpoint target (c) is to trigger considerations about early trial completion due to futility, where it is desired to reach a guideline based on (b) more easily/readily than a guideline based on (c). Accordingly, the results for (b) are interpreted focusing on the prior of  $PE = 60\%$  (i.e., scenario (i)), which makes it more likely to reach a guideline than the prior of  $PE = 0\%$ , and the results for (c) are interpreted focusing on the prior of  $PE = 0\%$  (i.e., scenario (ii)), which makes it less likely to reach a guideline than the prior of  $PE = 60\%$ . Results for (b) and (c) based on carrying forward the observed to-date infection rate in scenario (iii) provide additional guidance to the DSMB regarding considerations about enrollment modification or early trial completion.

Furthermore, a treatment-blinded report will be generated for distribution to the Leadership Group before each DSMB meeting takes place and will report estimates listed in (a)–(c) above calculated based only on treatment-blinded data in scenarios (i)–(iii). The reported results pertaining to estimates (a)–(c) under scenarios (i)–(iii) will be identical to those in the DSMB report.

While it is the primary responsibility of the Leadership Group to make decisions regarding trial operations and modifications based on the monitoring of treatment-blinded primary endpoints, given the resource issues involved, DSMB review is also needed because issues of scientific integrity are also involved. More specifically, the DSMB can evaluate the progress toward primary endpoint targets in the context of the treatment-unblinded data, and based on this review may recommend to the Leadership Group to complete the trial early due to reaching a guideline for futility to assess PE (specified below).

The monitoring for futility to assess PE includes the following guidelines for trial modifications:

- **Guideline for enrollment modifications.** If, in the  $PE = 60\%$  scenario for the prior distribution in (i), the estimated probability of reaching at least 57 total infections is less than 25%, the Leadership Group may consider enrollment modifications with the intention to be able to conduct the primary PE analysis with adequate power.

- **Guideline for futility.** If, in the PE = 0% scenario for the prior distribution in (ii), the estimated probability of reaching at least 21 total infections is less than 25%, the DSMB may recommend completing the trial early based on the inability to conduct the primary PE analysis with adequate power. However, since this is a proof-of-concept trial, a high bar is desired for completing the trial early for futility, and therefore if this event occurs yet the non-efficacy monitoring has not started or the non-efficacy boundary has not been reached, then this guideline for futility also requires that the estimated PE for the pooled VRC01 vs. control arm is < 30% and the estimated PE for the VRC01 30 mg/kg vs. control arm is < 30%.

If enrollment is incomplete at the time of an interim futility analysis, then the outlined estimation procedures will use the average observed enrollment rate in approximately the last 6 months for generating future enrollment data. A Bayesian approach will be used for generating future HIV-1 incidence data, conditional on observed data to-date. More specifically, the estimates in (a)–(c) will condition on the observed to-date treatment arm-pooled HIV-1 incidence rate, whereas the estimates in (d) will condition on the three observed to-date treatment arm-specific HIV-1 incidence rates. All estimates in (a)–(d) will also use the observed to-date treatment arm-pooled dropout rate for generating future dropout data. Further details of these calculations, including the prior distributions, are described in Section 9.4.1.

If, at any time, these guidelines for futility to assess PE are met and yet it appears that value exists in continuing the trial, the statisticians will provide the DSMB and the Leadership Group with additional information, as appropriate, for use in their consideration of whether to recommend early trial completion.

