The rationale for a Bayesian approach for the infection rate (see Section 9.4.2 for details) is to help stabilize the infection rate early in the trial when insufficient time will have passed to accrue many infections. If we were to rely solely on the observed infections, we might by chance obtain very low rates, which would lead to an unrealistic prediction of the number of endpoints.

We consider three different gamma prior distributions for the infection rate in each of scenarios (i)–(iii) reflecting different weights assigned to the prior distribution (see Section 9.4.2 for details). Gamma distributions are considered because they are conjugate to the exponential distribution used for generating future infection data.

At a given interim analysis,  $10^5$  trials are simulated using the above procedure and treatment arm-pooled infection and dropout rates for estimates in (a)–(c). Separately, another set of  $10^5$  trials is simulated using the above procedure, treatment arm-specific infection rates, and the treatment arm-pooled dropout rate for estimates in (d). Each of these trials yields a projected number of infections by the Week 80 visit. These projected numbers of infections from each trial will be used to estimate the entire distribution of the number of infections. The probability of reaching at least the target number of infections will be estimated as the proportion of trials with the projected number of infections greater than or equal to the target.

Figures on enrollment, HIV-1 incidence and dropout over time will also be included to aid interpretation of the results.

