#### 9.4.2 A Bayesian model for the HIV-1 incidence rate in estimation of the number of HIV-1 infection endpoints at an interim analysis

Let  $n_k$  and  $T_k$  denote, respectively, the infection count and the observed total person-time at risk at the time of the  $k$ -th futility analysis, pooling over all treatment arms. Additionally, let  $T^*$  denote the estimated total person-time at risk for the primary efficacy analysis. Let the prior distribution of the pooled HIV-1 incidence rate  $p$  be  $\text{Ga}(\alpha, \beta)$  parametrized such that the prior mean  $E p = \alpha/\beta$  (the same Bayesian method applies to the treatment arm-specific HIV-1 incidence rate).

Generally, assuming that, conditional on  $p$ , the times to infection follow  $\text{Exp}(p)$ , the posterior mean of  $p$  at the time of the  $k$ -th analysis equals

$$\begin{aligned} E[p | \text{data}] &= \frac{\alpha + n_k}{\beta + T_k} \\ &= \frac{\alpha}{\beta} \frac{\beta}{\beta + T_k} + \frac{n_k}{T_k} \frac{T_k}{\beta + T_k}, \end{aligned} \quad (4)$$

i.e., the posterior mean can be interpreted as a convex combination of the prior mean and the observed incidence rate. For a given  $\beta > 0$ , the weight on the prior mean at the first analysis depends on the accumulated person-time at risk ( $T_1$ ), and the weight will decrease in subsequent analyses because  $\beta/(\beta + T_k)$  is a decreasing function of  $T_k$ , which is a desirable Bayesian property.

In order to identify  $\alpha$  and  $\beta$ , it is desirable that the prior mean equals the pre-trial assumed treatment arm-pooled incidence rate  $p^*$  (e.g., under  $PE = 60\%$ ,  $p^* = (1/3) \times 0.055 + (2/3) \times 0.4 \times 0.055 = 0.033$  in HVTN 703/HPTN 081), i.e.,

$$\frac{\alpha}{\beta} = p^*.$$

Furthermore, we propose to consider three values of  $\beta$  that correspond to the weights  $w = \frac{1}{2}$ ,  $\frac{1}{3}$  and  $\frac{1}{4}$  on the prior mean at the time when 50% of the estimated total person-time at risk has been accumulated, i.e., for each value of  $w$ ,  $\beta$  is defined as the solution to the equation

$$\frac{\beta}{\beta + T^*/2} = w.$$

It follows that

$$\beta = \beta(w, T^*) = \frac{wT^*}{2(1-w)},$$

and the estimation of  $T^*$  is described in Section 9.4.2.1. For  $w = \frac{1}{2}$ ,  $\frac{1}{3}$  and  $\frac{1}{4}$ , we obtain  $\beta = \frac{T^*}{2}$ ,  $\frac{T^*}{4}$ , and  $\frac{T^*}{6}$ , respectively.

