At the  $k$ -th futility analysis and for each of the three values of  $\beta$ , we will sample the HIV-1 incidence rate from  $\text{Ga}(\alpha + n_k, \beta + T_k)$  for generating future data and report the weight  $\frac{\beta}{\beta + T_k}$  on the prior mean in the convex combination (4).

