#### 9.4.2.1 Estimation of the total person-years at risk ( $T^*$ )

We will use HVTN 703/HPTN 081 to illustrate the calculation. In this trial, the total target sample size is  $N = 1900$ , the duration of follow-up per participant is  $\tau = 80/52$  years, the pre-trial assumed dropout rate is  $d^* = 0.1$  dropouts per person-year at risk (PYR), and, in the  $PE = 60\%$  scenario, the pre-trial assumed treatment arm-pooled HIV-1 incidence rate is  $p^* = (1/3) \times 0.055 + (2/3) \times 0.4 \times 0.055 = 0.033$  cases per PYR.

We consider the standard right-censored failure time analysis framework. Denoting the failure and censoring times as  $T$  and  $C$ , respectively, we assume that  $T$  is independent of  $C$ ,  $T \sim \text{Exp}(p^*)$ , and  $C \sim \text{Exp}(d^*)$ . It follows that  $X := \min(T, C) \sim \text{Exp}(p^* + d^*)$  and

$$\begin{aligned} T^* &= N \times E[\min(X, \tau)] \\ &= N \times \{E[X \mid X \leq \tau] P(X \leq \tau) + \tau P(X > \tau)\} \\ &= N \times \left\{ (p^* + d^*) \int_0^\tau x \exp^{-(p^* + d^*)x} dx + \tau \exp^{-(p^* + d^*)\tau} \right\} \\ &= N \times \frac{1 - \exp^{-(p^* + d^*)\tau}}{p^* + d^*}. \end{aligned}$$

In HVTN 703/HPTN 081, this amounts to  $T^* = 2643.42$  PYRs. For comparison, if all  $N$  participants were followed for  $\tau$  years, the total PYRs would be  $N\tau = 2923.08$  years.

Subsequently, for  $T^* = 2643.42$  PYRs, if  $T_1 = 0.2T^*$ , the weights  $\frac{\beta}{\beta + T_1}$  on the prior mean at the first futility analysis corresponding to  $w = \frac{1}{2}, \frac{1}{3},$  and  $\frac{1}{4}$  are 0.71, 0.56, 0.45, respectively. If  $T_1 = 0.3T^*$ , the respective weights on the prior mean are 0.63, 0.45, and 0.36.

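### Futility scenario (iii) centres its prior on the observed infection rate and then updates it with the same data, so the projections it gives the DSMB look more certain than they are

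*SAP*

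**What the plan says.** SAP 9.4 reports the distribution of total infections, and the probabilities of reaching 57 and 21 with 95% credible intervals, under three scenarios. In (i) and (ii) the prior reflects PE = 60% and PE = 0%. In (iii) it is "the prior assumption that the infection rate equals the observed to-date infection rate". Scenario (iii) covers the arm-pooled outputs (a)–(c). Its results go to the DSMB as additional guidance and also into the treatment-blinded report for the Leadership Group.

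Three other statements matter:

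- SAP 9.4: estimates (a)–(c) "will condition on the observed to-date treatment arm-pooled HIV-1 incidence rate".
- SAP 9.4.1: "We consider three different gamma prior distributions for the infection rate in each of scenarios (i)–(iii").
- SAP 9.4.2: for each of the three β values, "we will sample the HIV-1 incidence rate from" a gamma distribution with shape α + n_k and rate β + T_k. Here n_k and T_k are the infections and person-time observed so far.

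On α, SAP 9.4.2 says only that "it is desirable that the prior mean equals the pre-trial assumed treatment arm-pooled incidence rate", written p*. The three β values give weights w = 1/2, 1/3 and 1/4 "on the prior mean at the time when 50% of the estimated total person-time at risk has been accumulated".

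**The concern.** A prior should bring information from outside the data that update it. In (i) and (ii) it does, because the prior mean comes from pre-trial assumptions. In (iii) the prior mean is the observed rate, and the same observations enter again through the likelihood. The prior then acts as β extra person-years that repeat what was already seen.

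SAP 9.4.1 justifies the Bayesian approach as stabilising the rate early, when few infections have accrued. In (iii) the prior cannot do that: it leaves the centre at the observed rate and only removes uncertainty. The three weights look like a sensitivity analysis, but here they vary only the amount of unearned precision. At stake is how certain the DSMB and Leadership Group think the carried-forward projection is, above all at early looks.

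**Working it through.** **1. Reproduce the SAP's figures.** SAP 9.4.2.1 gives T* = N(1 − exp(−(p*+d*)τ))/(p*+d*). For HVTN 703/HPTN 081, N = 1900, p* = 0.033, d* = 0.10 and τ = 80/52 give 2643.42 person-years, as stated. With β = T*/2, T*/4, T*/6, the prior weight β/(β+T_1) at T_1 = 0.2T* is 0.714, 0.556, 0.455. At 0.3T* it is 0.625, 0.455, 0.357. The SAP prints "are 0.71, 0.56, 0.45, respectively" and "the respective weights on the prior mean are 0.63, 0.45, and 0.36", so these agree. For HVTN 704/HPTN 085, N = 2700 and p* = 0.018 give T* = 3798.6.

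**2. Posterior for (iii).** Setting α/β = n_k/T_k gives α = βn_k/T_k, and the posterior is Ga(n_k(1+β/T_k), β+T_k).

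- Mean: n_k/T_k, unchanged.
- Effective number of events: n_k(1+β/T_k). At 0.2T* the multiplier is 3.50, 2.25, 1.83, so 14 infections act as 49, 31.5, 25.7.
- SD of the rate: data-only SD × √(T_k/(T_k+β)). At 0.2T* this factor is 0.53, 0.67, 0.74.

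**3. Projected total.** The SAP reports total infections, which also carry the chance variation of future events. With remaining person-time R = T* − T_k treated as fixed, the future count is negative binomial with variance (n_k/T_k)·R·(1 + R/(T_k+β)). Against using the data once (β = 0), the SD ratio is

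√{ [(T*+β)/(T_k+β)] / [T*/T_k] },

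which does not depend on n_k. At 0.2T* with β = T*/2 it is √{(1.5/0.7)/5} = 0.65.

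| T_k/T* | w = 1/2 | w = 1/3 | w = 1/4 |
|---|---|---|---|
| 0.20 | 0.65 | 0.75 | 0.80 |
| 0.30 | 0.75 | 0.83 | 0.87 |
| 0.43 | 0.83 | 0.89 | 0.92 |

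The fractions 0.2 and 0.3 are the SAP's own illustrations, given for HVTN 703/HPTN 081. The 43% is an assumption for the first HVTN 704/HPTN 085 report in April 2018. It lies inside a range of about 39–49% obtained from roughly uniform accrual between a first enrollment in March–July 2016 and a last enrollment in early October 2018.

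**4. Probability of reaching 57 (HVTN 704/HPTN 085).** Infection counts are assumed. The 29 matches Protocol Table 4-3 at week 104 under PE = 60% (16 + 13).

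| Infections, T_k/T* | Data used once | w = 1/2 | w = 1/3 | w = 1/4 |
|---|---|---|---|---|
| 14, 0.20 | 0.78 | 0.90 | 0.87 | 0.85 |
| 9, 0.20 | 0.185 | 0.101 | 0.128 | 0.142 |
| 29, 0.43 | 0.88 | 0.93 | 0.91 | 0.90 |

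With 14 infections at 20%, the 95% interval for the total is 42–107 with the data used once and 50–93 at w = 1/2; the mean is 70 in both. Simulated coverage of the nominal 95% prediction interval at 20% (true rate 0.018) is 81%, 86%, 88%, against about 95% with the data used once.

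**The case against.** Five points can be made on the other side.

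- **The double use is inferred.** SAP 9.4.2 defines the prior mean only as p*, and SAP 9.4.1 describes the prior as resting on pre-trial assumptions. This stands: the first defect is that α for (iii) is missing. But keeping p* would make (iii) no different from (i) or (ii), and using no informative prior would contradict the three gamma priors of 9.4.1. Centring on n_k/T_k is the reading that fits.
- **The rate's SD ratio is not what the DSMB sees.** A reader might take 0.53, 0.67, 0.74 as the narrowing of the reported projection. It is not: SAP 9.4 lists no interval for the rate, and the total narrows less.
- **20% is earlier than this trial's first futility report.** On the accrual assumption above this is right, and the effect near 43% is modest. SAP 8 also shows that this version postdates last enrollment. By then about 64–70% of person-time had accrued, and the ratios are about 0.92–0.97.
- **No decision rule is touched.** A reader might infer that the double use could tip the 25% threshold: with 10 infections at 20%, P(≥57) goes from 29.3% to 23.2% at w = 1/2. SAP 9.4 attaches that threshold to scenario (i) for 57 infections and (ii) for 21, never to (iii), so the crossing carries no decision weight.
- **Scenario (iii) is a simple current-trend projection.** Dropout and enrollment rates are also plugged in as point estimates. That is fair, but the SAP attaches 95% credible intervals to its reach-probabilities, and those should not rest on repeated data.

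**Conclusion.** The point holds as a limited one. As best read, scenario (iii) counts the observed infections twice. The projection is not biased, because its mean is unchanged. Its uncertainty is understated and its reach-probabilities are pushed away from the middle. The SD of the projected total is about 20–35% too small at 20% of person-time and 8–17% too small near 43%, and the effect fades as data accrue. The probability of reaching 21 is hardly affected unless incidence is very low.

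The documents do not support a claim that the primary analysis, type I error or either formal futility guideline is affected. What is affected is the supplementary guidance to the DSMB and the blinded Leadership Group report.

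The SD ratios rest on α = βn_k/T_k, on the stated person-time fractions and on fixed remaining person-time. The probabilities also depend on the assumed counts.

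**What to change.** In SAP 9.4.2, write out the prior for scenario (iii). State that the rate is sampled from a vague-prior posterior such as Ga(n_k + 0.5, T_k), and that the three prior weights apply to (i) and (ii) only. Amend the sentence in SAP 9.4.1 that gives all three scenarios three gamma priors.

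The half event keeps the distribution proper if no infection has been seen. It raises the projected mean slightly: with 14 infections at 20%, R/T_k = 4, so the mean is 14 + 14.5 × 4 = 72 instead of 70. Ga(n_k, T_k) avoids that shift once n_k > 0.

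The cost is about a line of text and code, one set of results for (iii) instead of three, and wider intervals.

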#### 9.4.1 Estimation of the number of HIV-1 infection endpoints at an interim analysis

The method for estimating the probability distribution of the number of HIV-1 infection endpoints by the Week 80 visit is based on the following approach to simulating this trial. The trial is modeled as a combination of three processes—enrollment, dropout, and HIV-1 infection—and a large number of trials is simulated. The three processes are assumed to be independent, and their distributions are taken to be Poisson, exponential, and exponential, respectively. Data are generated at the level of the individual participant, such that, for each participant, we obtain an enrollment time, an (underlying true) infection time, and a dropout time. Only the minimum of the infection and dropout times is observable, and the average value for this minimum is beyond the duration of the trial, such that neither event will be observed for most participants.

In the absence of observed trial data, the treatment arm-pooled as well as the treatment arm-specific parameters for the infection and dropout processes are chosen to match our pre-trial assumptions about these rates. In addition, the infection rate considers both the

design alternative of  $PE = 60\%$  and the null hypothesis of  $PE = 0\%$  in the calculation of the total and treatment arm-specific numbers of endpoints. More specifically, in HVTN 704/HPTN 085, treatment arm-pooled calculations in (a)–(c) assume

- pooled infection rate ( $PE = 60\%$  scenario):  $(1/3) \times 0.03 + (2/3) \times 0.4 \times 0.03 = 0.018$  infections/person-year at-risk, and
- pooled infection rate ( $PE = 0\%$  scenario): 0.03 infections/person-year at-risk,

and, in HVTN 703/HPTN 081,

- pooled infection rate ( $PE = 60\%$  scenario):  $(1/3) \times 0.055 + (2/3) \times 0.4 \times 0.055 = 0.033$  infections/person-year at-risk, and
- pooled infection rate ( $PE = 0\%$  scenario): 0.055 infections/person-year at-risk.

Both trials assume a treatment arm-pooled dropout rate of 0.10 dropouts/person-year at-risk.

In HVTN 704/HPTN 085, treatment arm-specific calculations in (d) assume

- infection rate in the control arm: 0.03 infections/person-year at-risk,
- infection rate in each VRC01 arm ( $PE = 60\%$  scenario):  $0.4 \times 0.03 = 0.012$  infections/person-year at-risk, and
- infection rate in each VRC01 arm ( $PE = 0\%$  scenario): 0.03 infections/person-year at-risk,

and, in HVTN 703/HPTN 081,

- infection rate in the control arm: 0.055 infections/person-year at-risk,
- infection rate in each VRC01 arm ( $PE = 60\%$  scenario):  $0.4 \times 0.055 = 0.022$  infections/person-year at-risk, and
- infection rate in each VRC01 arm ( $PE = 0\%$  scenario): 0.055 infections/person-year at-risk.

In the absence of observed data, in both trials and each of the three treatment arms, the dropout rate is assumed to be 0.10 dropouts/person-year at-risk.

The first step in simulating each trial is to enroll a certain number of participants per week according to a random draw from a Poisson distribution with rate parameter as listed above. Enrollment continues week-by-week until a total of 2700 participants in HVTN

704/HPTN 085 or 1900 participants in HVTN 703/HPTN 081 is reached. Second, each participant is assigned an exact enrollment day, uniformly distributed within their enrollment week. Following enrollment, the infection and dropout times are drawn from their respective exponential distributions, and the lesser of the two is recorded as occurring at the given time (possibly outside the time-window of the trial). We consider dropout events to have occurred at the dropout time (in weeks) that was generated (assuming it was less than the infection time). For participants who become HIV-1 infected, we record their time of diagnosis as the time of the first study visit following the true infection time. It is this time of diagnosis that we observe for infected participants.

A modification of the above procedure for simulating an efficacy trial is used for estimating metrics of futility to assess PE at a given interim analysis. The modification entails using the observed trial data to estimate parameters of the processes, rather than relying entirely on pre-trial assumptions. In particular:

- enrollment rate: if enrollment is incomplete, estimated based on the treatment arm-pooled rate observed in approximately the last 6 months in the study,
- infection rate: drawn from a posterior distribution of the infection rate formed by combining the observed data with our prior specification about the infection rate based on the pre-trial assumptions, and
- dropout rate: estimated based on the treatment arm-pooled rate observed to date.

The rationale for a Bayesian approach for the infection rate (see Section 9.4.2 for details) is to help stabilize the infection rate early in the trial when insufficient time will have passed to accrue many infections. If we were to rely solely on the observed infections, we might by chance obtain very low rates, which would lead to an unrealistic prediction of the number of endpoints.

We consider three different gamma prior distributions for the infection rate in each of scenarios (i)–(iii) reflecting different weights assigned to the prior distribution (see Section 9.4.2 for details). Gamma distributions are considered because they are conjugate to the exponential distribution used for generating future infection data.

At a given interim analysis,  $10^5$  trials are simulated using the above procedure and treatment arm-pooled infection and dropout rates for estimates in (a)–(c). Separately, another set of  $10^5$  trials is simulated using the above procedure, treatment arm-specific infection rates, and the treatment arm-pooled dropout rate for estimates in (d). Each of these trials yields a projected number of infections by the Week 80 visit. These projected numbers of infections from each trial will be used to estimate the entire distribution of the number of infections. The probability of reaching at least the target number of infections will be estimated as the proportion of trials with the projected number of infections greater than or equal to the target.

Figures on enrollment, HIV-1 incidence and dropout over time will also be included to aid interpretation of the results.

